5.3 Demographic and Baseline Characteristics

Subject demographic and disease characteristics (age, age group (6-11, 12-17, and ≥ 18 years), gender, race, ethnicity, height, weight, body mass index, six minute walk distance, six minute walk distance groups (<300 meters, ≥ 300 - <400 meters, ≥ 400 meters), time to run/walk 10 meter, time to stand from supine, time to stand from supine ($<5s$, $\geq 5s$), corticosteroid use (Yes/No), and ambulatory/non-ambulatory) will be summarized for overall subjects, a subgroup of subjects with corticosteroid use (Yes/No), baseline six minute walk distance groups (<300 meters, ≥ 300 - <400 meters, ≥ 400 meters), baseline time to stand from supine groups ($<5s$, $\geq 5s$), and a subgroup of ambulatory/non-ambulatory subjects at study entry.

5.3.1 Brook Upper Function Rating

The number of subjects with each baseline Brook Upper Function Rating score will be tabulated by the corticosteroid use (Yes/No). Subjects' mean age of each baseline score will be summarized as well.

5.4 Clinical History

Clinical history will be coded using the Medical Dictionary for Regulatory Activities (MedDRA Version 20.1). The count and percentage of subjects under each history term, coded by system organ class (SOC) and preferred term (PT), will be summarized.

5.5 Concomitant Medications and Procedures

Prior medications and concomitant medications will be coded using the World Health Organization Drug Dictionary (WHODRUG) dictionary dated 2017DEC01 into Anatomical-Therapeutic-Chemical (ATC) classification codes. The prior medications are defined as any medications that subjects started before the first dose date. Concomitant medications are defined as any medications that subjects took after/on the first dose date. The prior and concomitant medications will be summarized by ATC level 3 and preferred terms. The concomitant cardiac medications will be summarized similarly.

Specific attention will be focused on corticosteroid use. The numbers of subjects receiving/not-receiving corticosteroids at baseline or during the study, switching from receiving to not receiving or vice versa, switching in different types of corticosteroids, and duration of corticosteroid use during the study and by type will be summarized.

The prior and concomitant non-drug therapies will be defined similar to the prior and concomitant medications. They will be coded by MedDRA Version 20.1 and summarized by SOC and PT.

5.7 Primary Variables

5.7.1 Adverse Events

Adverse events will be classified using MedDRA Version 20.1 classification system. The severity of adverse events will be graded by the investigator according to the CTCAE, Version 3.0 whenever possible. A treatment-emergent adverse event (TEAE) is defined as an adverse event that occurs or worsens in the period extending from the day of a subject's first dose of study drug to 6 weeks after the last dose of study drug in this study.

If a subject has multiple events under any given SOC and PT, the subject will be counted only once under that SOC and PT. If a subject has the same AE on multiple occasions, the highest severity (fetal, life-threatening, severe, moderate, and mild) recorded for the event will be presented and the highest drug relationship (1 = 'Unrelated', 2 = 'Unlikely', 3 = 'Possibly', 4 = 'Probably', 5 = 'Related'), reclassified into Related ('Possibly Related', 'Probably Related', 'Related') or Not Related ('Unrelated' and 'Unlikely'), will be presented on the respective tables.

Total numbers of AEs, TEAEs and serious AEs (SAE) and the number and percentage of subjects experiencing ≥ 1 TEAE, ≥ 1 SAE, discontinuation due to AE, and death will be tabulated. The number and percentage of subjects with TEAEs and SAEs will be by relationship to study drug and CTCAE/severity, respectively.

The number and percentage of subjects experiencing a specific TEAE will be tabulated

- by SOC, and PT
- by SOC, PT, and CTCAE/severity grade
- by SOC in the descending order of the SOC frequency in ataluren group
- by PT in the descending order of the PT frequency in ataluren group.

The following TEAEs will be analyzed similarly:

- by SOC, and PT and
- by SOC, PT, and CTCAE/severity grade.
 - i. Possibly or probably treatment-related TEAEs
 - ii. Possibly treatment-related TEAEs
 - iii. Probably treatment-related TEAEs
 - iv. Serious TEAEs and possibly or probably treatment-related serious TEAEs
 - v. TEAEs leading to discontinuation from treatment
 - vi. Hepatic and renal TEAEs and possibly or probably treatment-related hepatic and renal TEAEs leading to special diagnosis evaluation
 - vii. TEAEs with CTCAE/severity grade ≥ 3 and possibly or probably treatment-related TEAEs with CTCAE/severity grade ≥ 3
 - viii. Common TEAEs (subject frequency of $\geq 5\%$)

Listings of death, serious AEs, AEs leading to discontinuation from treatment, and hepatic and renal AEs leading to special diagnostic evaluations will be provided.

The drug exposure adjusted TEAE incidence rate will be summarized by SOC and PT, where the incidence rate of the TEAE per 100 patient-year = (number of events/number of patient-years) *100. The number of patient-years is defined as the sum of the number of days on study drug of all patients divided by 336. That is, a year is defined as 48 weeks.

In addition, the number of subjects with clinical laboratory abnormalities, abnormal vital signs, and abnormal electrocardiogram reported as TEAE will be summarized.

Non-serious TEAE will be displayed by SOC and PT. The common non-serious TEAE (subject frequency of $\geq 5\%$) will also be displayed by SOC and PT.

Numbers of occurrence of serious TEAE and the numbers of occurrence of non-serious TEAE will be summarized by SOC and PT, separately.

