10.4.5. Primary Variables

10.4.5.1. Adverse Events

Adverse events will be classified using the MedDRA classification system. The severity of adverse events will be graded by the investigator according to the CTCAE, Version 3.0 whenever possible. A treatment-emergent adverse event is defined as an adverse event that occurs or worsens in the period extending from the day of a patient's first ataluren dose in this study to 6 weeks after the last ataluren dose in this study.

The frequency of patients experiencing a specific adverse event will be tabulated by visit, body system, and MedDRA term. In the by-patient analysis, a patient having the same event more than once will be counted only once using the worst CTCAE grade.

Adverse events classified as CTCAE Grade 3 or higher; study-drug-related events; adrenal, hepatic, and renal events leading to special diagnostic evaluations; events leading to discontinuation from treatment; and SAEs will be considered with special attention.

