10.4.5.2. Laboratory Data

Hematological, serum biochemistry, adrenal laboratories, and urine data and their changes (only for continuous laboratory parameters) from baseline will be summarized by visit. Hematological, serum biochemistry, adrenal laboratories, and urine data will be graded according to CTCAE severity grade when applicable. For parameters for which a CTCAE scale does not exist, the frequency of patients with values below, within, and above the normal ranges will be summarized. Summary tables will be presented for each relevant assay to show the number of patients by severity grade with corresponding percentages. Subjects will be characterized only once for a given assay, based on their worst severity grade observed during the time period of interest.

Shift tables for hematology, serum biochemistry, adrenal laboratories, and urine data will also be presented showing change in CTCAE severity grade from baseline to each visit. For parameters for which a CTCAE scale does not exist, shift tables will be presented showing change in results from baseline (normal, low and high [or abnormal]) to each visit (normal, low and high [or abnormal]).

Separate listings and tables will be created for parameters for assessment of adrenal, hepatic, and renal monitoring based on the conditions listed in Section 6.3.

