13.2.3. Safety Monitoring

In response to the occurrence of mild transaminase elevations in healthy volunteers participating in Phase 1 studies, and adrenal and renal findings in individual toxicology species, a specific safety monitoring plan for the target organs that these types of abnormalities represent has been established in this study. In addition, thresholds for evaluation and intervention have been established for other types of adverse events or laboratory abnormalities observed in the study. The intent is to protect patients, obtain a thorough assessment of any clinically relevant adverse events or laboratory abnormalities, and to offer recommendations for interruption and dose modification of ataluren in response to potential safety signals. The nature of these risks and the measures to monitor for them are to be reflected in the informed consent form.

As noted in Section 6.3.1, patients must be monitored closely for adverse events or laboratory abnormalities during the course of the study, safety findings deserving particular attention include hepatic, adrenal, renal, and electrolyte abnormalities. Section 6.3.1 provides information on actions to be taken in the event that abnormalities are noted on specified monitoring studies. Thresholds are provided for interrupting ataluren immediately, for interrupting ataluren after confirmation of a value beyond the threshold, or for continuing ataluren while evaluating for potential drug-related toxicity.

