3.3 Study Endpoints

Primary:

- Safety profile characterized by type, frequency, severity, timing, and relationship to ataluren of any adverse events or laboratory abnormalities

Secondary:

- In ambulatory subjects,
 - i. change from baseline in 6MWD as measured by the 6-minute walk test (6MWT)
 - ii. change from baseline in physical function as measured by the North Star Ambulatory Assessment (NSAA)
 - iii. change from baseline in timed function tests (time to stand from supine and time to run/walk 10 meters)
- In non-ambulatory subjects,
 - i. change from baseline in pulmonary function test - % predicated forced vital capacity (FVC) and % predicted forced expiratory volume in 1 second (FEV1) as measured by spirometry
 - ii. change from baseline in patient and parent/caregiver-reported activities of daily living, as measured by the Egen Klassifikation (EK) scale

- All subjects,
 - i. changes in patient and/or parent/caregiver reports of disease status as measured by a standardized survey administered by site personnel

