5.7.2 Laboratory Tests

Hematological, serum biochemistry, adrenal laboratories, and urine data and their changes (only for continuous laboratory parameters) from baseline will be summarized by visit.

Shift tables for hematology and biochemistry data will also be presented showing change in CTCAE severity grade from baseline to each visit. For parameters for which a CTCAE scale does not exist, shift tables will be presented showing change in results from baseline (normal, low and high [or abnormal]) to each visit (normal, low and high [or abnormal]).

Summary of abnormalities in laboratory variables pre-defined for safety monitoring will be done per the following Table 2.

Table 2: Safety Monitoring Parameters and Actions to be Taken

Organ System and Laboratory Parameter	Stop Study Drug Immediately, Confirm Abnormal Value, and Then Start Work-Up	Stop Study Drug After Confirming ^a Abnormal Value, and Then Start Work-Up	Continue Study Drug, Confirm Abnormal Value, and then Start Work-Up ^a
Hepatic			
Serum total bilirubin	\geq Grade 3 ($\geq 3.0 \times$ ULN)	Grade 2 (1.5 – 3.0 x ULN)	---
Serum GGT	\geq Grade 3 ($\geq 5.0 \times$ ULN)	Grade 2 ($>2.5 - 5.0 \times$ ULN)	---
Serum ALT			\uparrow of >150 U/L with stable or \downarrow CK
Adrenal			
Plasma ACTH	---	$>$ ULN (and plasma cortisol $<$ LLN)	$>$ ULN (and cortisol WNL)
Renal			
Serum cystatin C	>2.00 mg/L	$>1.33 - 2.00$ mg/L	---
Serum creatinine	\geq Grade 2 ($\geq 1.5 \times$ ULN for age)	Grade 1 ($>$ ULN – $1.5 \times$ ULN for age)	---
Serum BUN	$\geq 3.0 \times$ ULN	$\geq 1.5 - 3.0 \times$ ULN	---
Urine protein: urine creatinine (spot)	---	>0.40 mg:mg	---
Urine protein: urine osmolality (spot)	---	>0.30 mg/L:mOsm/kg	---
Urine blood (by dipstick)	4+ (Large)	3+ (Moderate)	2+ (Small)

Organ System and Laboratory Parameter	Stop Study Drug Immediately, Confirm Abnormal Value, and Then Start Work-Up	Stop Study Drug After Confirming ^a Abnormal Value, and Then Start Work-Up	Continue Study Drug, Confirm Abnormal Value, and then Start Work-Up ^a
Serum electrolytes	Grade 3-4	Grade 2	Grade 1
Serum Na ⁺ , high	>155 mmol/L	>150 – 155 mmol/L	---
Serum Na ⁺ , low	<130 mmol/L	---	---
Serum K ⁺ , high	>6.0 mmol/L	>5.5 – 6.0 mmol/L	---
Serum K ⁺ , low	<3.0 mmol/L	---	---
Serum Mg ²⁺ , high	>1.23 mmol/L	---	---
Serum Mg ²⁺ , low	<0.4 mmol/L	<0.5 – 0.4 mmol/L	---
Total serum Ca ²⁺ , high	>3.1 mmol/L	>2.9 – 3.1 mmol/L	---
Total serum Ca ²⁺ , low	<1.75 mmol/L	<2.0 – 1.75 mmol/L	---

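### Without declaring it, the SAP leaves adrenal events out of the special-evaluation safety output, and adrenal and urine data out of the shift tables, that the protocol plans

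*SAP*

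**What the plan says.** The primary endpoint in SAP section 3.3 is "Safety profile characterized by type, frequency, severity, timing, and relationship to ataluren of any adverse events or laboratory abnormalities".

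**Adverse events.** Protocol section 10.4.5.1 lists the classes of event that deserve special attention, among them "adrenal, hepatic, and renal events leading to special diagnostic evaluations". SAP section 5.7.1 turns that list into tables. Item vi reads "Hepatic and renal TEAEs and possibly or probably treatment-related hepatic and renal TEAEs leading to special diagnosis evaluation". The listings planned later in the same section include "hepatic and renal AEs leading to special diagnostic evaluations will be provided". Neither place mentions adrenal events.

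**Laboratory data.** Protocol section 10.4.5.2 states: "Shift tables for hematology, serum biochemistry, adrenal laboratories, and urine data will also be presented". The corresponding sentence in SAP section 5.7.2 is "Shift tables for hematology and biochemistry data will also be presented".

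**Precedence and declared changes.** SAP section 1 states that the SAP prevails over the protocol where they conflict. SAP section 7, which records departures from the protocol, mentions the removal of paired t-tests from the functional and spirometry endpoints and the addition of subgroup analyses. It says nothing about adrenal events or shift tables.

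**The concern.** Adrenal function is not an incidental safety topic here. Protocol section 13.2.3 explains that the transaminase elevations in Phase 1 and "adrenal and renal findings in individual toxicology species, a specific safety monitoring plan for the target organs" are why the monitoring plan exists. Section 13.2.3.2.1 describes adrenal cortical findings in dogs that had not reversed after 4 and 8 weeks of recovery. It puts the no-adverse-effect exposure for adrenal cortical function at about 0.8 times the patient exposure, and says that patients could experience similar events.

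If the SAP is followed as written, the report will show which hepatic and renal events led to a diagnostic work-up but not which adrenal events did. Tables by system organ class and preferred term cannot recover this, because they do not mark events by whether they triggered an evaluation. Without shift tables, no planned table for the adrenal and urine panels relates a patient's value to his own baseline category. Because the SAP takes precedence and declares no change, a reader of the report would have no sign that anything planned had been left out.

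**Working it through.** No arithmetic result is in question. The check is an item-by-item comparison of planned outputs, followed by a look at what the remaining outputs capture.

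**Step 1. Outputs side by side.**

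| Output | Protocol | SAP | Missing from SAP |
|---|---|---|---|
| Events that triggered a work-up | 3 organs: adrenal, hepatic, renal (10.4.5.1) | Table: 2 organs; listing: 2 organs (5.7.1) | Adrenal, in both |
| Shift tables | 4 panels: hematology, biochemistry, adrenal, urine (10.4.5.2) | 2 panels: hematology, biochemistry (5.7.2) | Adrenal, urine |
| By-visit summaries and changes | 4 panels (10.4.5.2) | 4 panels (5.7.2) | None |
| Laboratory thresholds for organ monitoring | Adrenal, hepatic, renal (10.4.5.2, referring to 6.3) | Table 2 has all three blocks (5.7.2) | None apparent |

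Of the two omissions, section 7 declares 0.

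**Step 2. Is the adverse event gap isolated?** The other classes in protocol 10.4.5.1 all reach SAP 5.7.1: drug-related events (items i to iii), serious events (iv), events leading to discontinuation (v) and Grade 3 or higher (vii). Adrenal is the only element of the protocol's list that did not carry over.

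**Step 3. Is the shift-table gap real?** The first sentence of SAP 5.7.2 names all four panels for the by-visit summaries; the shift-table sentence that follows names two. The sentence after that, on parameters without a CTCAE scale, sets no panel limit. The protocol has the same sentence directly after its four-panel list, so it describes the format for ungraded parameters and does not set the scope. The natural reading is that two panels were removed.

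**Step 4. Does Table 2 replace the adrenal shifts?** Its adrenal row counts ACTH above the upper limit with cortisol either below the lower limit or within limits. Classing each marker as low, normal or high gives 3 × 3 = 9 combinations. Table 2 counts 2 of them, both with high ACTH. Low cortisol with normal or low ACTH is not counted, and baseline plays no part.

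**Step 5. Does Table 2 replace the urine shifts?** It flags protein:creatinine above 0.40 and protein:osmolality above 0.30. Protocol section 13.2.3.3.2 describes values from 0.2 and 0.15 as abnormal. The ratios are 0.40/0.2 = 2 and 0.30/0.15 = 2. Assuming the reference limits used for shifts follow those lower values, which the documents do not state, a move from normal to between one and two times the limit would appear in a shift table but not in Table 2. Several urinalysis items in protocol section 7.2.13, such as glucose, ketones and leukocytes, have no row in Table 2.

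**Step 6. Are the adrenal data available?** Protocol Table 5 schedules 23 ACTH and 23 cortisol samples per patient at 2 mL each: 23 × 2 + 23 × 2 = 92 mL of a planned 264.5 mL, and 92/264.5 = 35%. The data are there; only the presentation is missing.

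**The case against.** The strongest reply is that little information is lost. Adrenal events still enter the general tables: by organ class and term, by severity, related, serious, Grade 3 or higher, leading to discontinuation, and exposure-adjusted rates. Laboratory abnormalities reported as adverse events are summarized, and by-patient listings are planned for each CRF module (SAP 5.1). All of this stands. A reader might infer that adrenal safety has vanished from the analysis; the documents do not support that.

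Nor is it right to infer that by-visit means are the only view of ACTH and proteinuria. Table 2 summarizes threshold abnormalities in exactly these parameters, and its adrenal row matches the pattern that protocol section 13.2.3.2.2 treats as the early sign of primary failure, raised ACTH with normal or falling cortisol. The same section expects low cortisol in boys taking corticosteroids, so the uncounted pattern says less about the drug in them. That narrows the loss but does not remove it: the explanation is not available for boys not on corticosteroids, and SAP 5.1 already splits analyses by corticosteroid use, so a shift table would separate the two groups.

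On the adverse event side, the protocol promises special attention and does not prescribe a table or listing; only the shift tables are an explicit protocol output. This is correct. However, the SAP chose tables and a listing as its way of giving that attention and then left out one of the three organs.

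Finally, the sentence on ungraded parameters could be read to cover adrenal and urine data. That reading is possible but less likely, for the reason in Step 3. If it is what was intended, the text should say so.

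**Conclusion.** The point holds in a limited form. As written, the SAP omits adrenal from the table and listing of events that led to a diagnostic work-up (two organs where the protocol names three). On its natural reading, it also omits adrenal laboratories and urine from the shift tables (two panels where the protocol requires four). Neither omission is declared, and the SAP's own precedence rule makes the narrower text govern. The label is wrong as written: an undeclared conflict with the protocol.

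What is lost is the adrenal special-evaluation output and the patient-level shifts from baseline to each visit, for instance to low cortisol without raised ACTH. No estimate, test or sample size is affected. A reader might also infer that a shift from baseline to the worst value is due; the protocol's shift tables run from baseline to each visit only, and worst grade belongs to a separate frequency summary there. The documents give no reason for the omissions, so nothing should be inferred about intent.

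The conclusion on shift tables rests on the natural reading of SAP 5.7.2. The urine example also assumes that the reference limits follow the values given in protocol section 13.2.3.3.2.

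**What to change.** In SAP 5.7.1, add adrenal to item vi and to the listing of events that led to a diagnostic evaluation. In SAP 5.7.2, name adrenal laboratories and urine in the shift-table sentence, with shifts from baseline to each visit by CTCAE grade where a scale exists and by normal, low and high (or abnormal) where it does not.

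If the sponsor prefers to leave any of this out, section 7 should list the omission and give the reason. That would settle the conflict between the documents but would not recover the lost outputs, so restoring them is the better course.

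The cost is a few extra tables and one wider listing. No new data, visits or clinical rules are needed, and the Table 2 thresholds are not in question here.

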7.2.1.4 Post-Treatment Visits

All patients who discontinue at luren must return for a Post-Treatment Visit at the investigator site 6 weeks (±7 days) after the last dose of at luren for final study-related evaluations. If the End-of-Treatment Visit occurs >6 weeks after the last dose of at luren, the Post-Treatment Visit does not need to be performed. For patients discontinuing the study to transition to commercially available at luren, an End-of-Treatment visit should be performed for that patient. However, a 6-Week Post-Treatment Visit is not required for these patients.

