1 OVERVIEW

This statistical analysis plan (SAP) details the statistical methods to be used in the analyses and presentation of the data collected in Study PTC124-GD-019-DMD, also referred to as Study 019. Preparation of this SAP incorporates statistical design elements present in the protocol Version 5.0 (dated 18 November 2015). Details are documented in Sections 1-7.

In addition to the protocol defined analyses, a natural history control using the Cooperative International Neuromuscular Research Group (CINRG) will be utilized in order to help to better understand the long-term ataluren data. The planned analysis will be presented in Section 8.

After the implement of protocol Version 5.0, the sponsor has developed the protocol Version 6.1 (dated 08 March 2017) specifically for Canadian sites only for ethics approval when they finished all visits per Version 5.0 and were waiting to roll into another open-label nmDMD Study PTC124-GD-016-DMD conducted in the United States (US). The maximal scheduled visit in Version 5.0 was extended from week 240 to week 336 in Version 6.1. All data collected based on both Versions will be summarized together.

Where conflicts exist between this SAP and the study protocols, the information contained in this SAP supersedes the protocol.

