2 STUDY DESIGN

This study comprises a Phase 3, open-label study of ataluren in subjects with nmDBMD who previously received ataluren at an investigator site in a prior PTC-sponsored clinical study. A separate open-label study (PTC124-GD-016-DMD) is being conducted for nmDBMD subjects who previously received ataluren at an investigator site in the US.

All participating sites must have had at least 1 subject that received ataluren treatment in a prior

PTC-sponsored clinical study in DBMD. It is planned that up to ~96 subjects will be enrolled.

Subjects will receive ataluren 3 times per day (TID) at respective morning, midday, and evening doses of 10 mg/kg, 10 mg/kg, and 20 mg/kg, for approximately 240 weeks. Study assessments will be performed at clinic visits during screening, on the first day of ataluren dosing, and then every 12 weeks during the ataluren treatment period.

The proposed types and timing of data to be recorded are described in [Table 1](#) below based on protocol Version 5.0.

Table 1: Schedule of Events

Period	Screening ^a	Baseline ^a	Ataluren Treatment					Post-Treatment
	-4 to -1	Week 1	Every 60 Weeks	Every 12 Weeks	Every 24 Weeks	Every 48 Weeks	End of Tx Week 240	6 Week Post D/C
Informed Consent {7.2.2}	X							
Clinical/medication history	X							
Hepatitis screen	X							
Vital signs	X	X		X			X	X
Brooke UE Functional Rating Scale	X							
Height/Ulna length/Arm Span	X				X		X	
Physical examination	X					X	X	
Weight	X	X		X			X	X
Hematology	X	X		X			X	X
Biochemistry	X	X		X			X	X
ACTH and cortisol	X	X		X			X	X
Renin and aldosterone	X	As Indicated						
Urinalysis	X	X		X			X	X
12-lead ECG	X	As Indicated						
Echocardiogram	X		X			X		X ^b
6-minute walk test	X				X		X	
Timed Function Tests	X					X	X	
North Star Ambulatory Assessment	X					X	X	
Egen Klassifikation Scale	X					X	X	
Spirometry	X				X		X	
Disease status survey	X	X		X			X	
Drug administration		X		X				
Drug compliance				X			X	
Adverse events		X		X			X	X
Concomitant medications	X	X		X			X	X

a Ataluren may be initiated as soon as the investigator confirms patient eligibility. Baseline procedures (excluding drug administration) do not need to be performed if Screening procedures have been performed within 7 days of anticipated initiation of ataluren treatment.

b Only applies to patients who discontinue the study after 240 weeks of treatment.

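### The exposure-adjusted TEAE rate in SAP 5.7.1 counts events to 6 weeks after the last dose but only on-drug days, so it runs slightly high (about 2.5% at 240 weeks)

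*SAP*

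**What the plan says.** SAP 5.7.1 defines a TEAE as an event that occurs or worsens from the first dose "to 6 weeks after the last dose of study drug in this study". It then gives the rate: "the incidence rate of the TEAE per 100 patient-year = (number of events/number of patient-years) *100". The denominator follows: "The number of patient-years is defined as the sum of the number of days on study drug of all patients divided by 336". The unit is declared openly: "That is, a year is defined as 48 weeks".

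The off-drug window is observed. The protocol's schedule of events and section 7.2.24 collect adverse events at the 6-week Post-Treatment Visit, and section 8.8 closes the reporting period there. Section 7.2.1.4 requires that visit of boys who discontinue ataluren, with exceptions. For boys transferring to commercial drug it says: "However, a 6-Week Post-Treatment Visit is not required for these patients".

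Nothing in the SAP adds the 6 weeks to the denominator or limits the rate to on-drug events. SAP 5.6 takes the off-treatment gap of the re-enrolled subject out of treatment duration, but the TEAE window has no corresponding rule.

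**The concern.** An incidence rate needs events and person-time from the same period. Here the numerator covers treatment plus 6 weeks and the denominator covers treatment only. Safety is the primary endpoint, and the other adverse-event summaries in SAP 5.7.1 are counts and percentages, so this rate is the only one there that adjusts for exposure.

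Exposure will vary. Planned treatment runs "for approximately 240 weeks", some Canadian boys continue longer ("The maximal scheduled visit in Version 5.0 was extended from week 240 to week 336 in Version 6.1"), boys may leave early, and SAP 5.2 records that the sponsor decided to end the study. SAP 5.1 asks for analyses by corticosteroid use and ambulatory status, and protocol 10.3 allows the data to be read alongside other ataluren studies. An excess that depends on exposure could slightly affect such comparisons wherever mean exposure differs.

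**Working it through.** **Inputs.** Off-drug window: 6 weeks = 42 days (SAP 5.7.1). Planned treatment: 240 weeks = 1680 days (SAP 2). Enrolment: "It is planned that up to ~96 subjects will be enrolled" (SAP 2). Longest schedule: 336 weeks = 2352 days (SAP 1).

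**The plan's own figure.** 48 × 7 = 336 days, which agrees with the SAP. The documents state no TEAE rate to reproduce.

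**Formula.** For a boy treated T days and then observed for 42, the rate as defined divided by a rate with matched person-time is (T + 42)/T. Pooled over boys it is 1 + 42/mean(T). Against the matched denominator this depends only on person-time. It also equals the excess over the on-drug rate if events occur at the same rate off drug as on drug.

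**At the planned duration.** 96 × 1680/336 = 480 patient-years on drug. 96 × 1722/336 = 492 with the window. 492/480 = 1.025, an excess of 2.5%.

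**Other mean exposures.**

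| Mean weeks on drug | 42/mean days | Excess |
|---|---|---|
| 336 | 42/2352 | 1.8% |
| 240 | 42/1680 | 2.5% |
| 150 | 42/1050 | 4.0% |
| 96 | 42/672 | 6.25% |
| 48 | 42/336 | 12.5% |
| 24 | 42/168 | 25% |

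The last two rows are hypothetical upper bounds for a group with that mean exposure.

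**Fewer events off drug (assumption: half the on-drug rate).** The excess over the on-drug rate halves: 21/1680 = 1.25% at 240 weeks and 21/168 = 12.5% at 24 weeks.

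**Early stopping (assumption: a share stops at 24 weeks and the rest reach 240).**
- 25% stop: the mean is 186 weeks and the excess is 6/186 = 3.2%.
- 50% stop: the mean is 132 weeks and the excess is 6/132 = 4.5%.
- If those early stoppers have no off-drug follow-up, the excess is 0.75 × 6/186 = 2.4% and 0.50 × 6/132 = 2.3%.

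**Subgroup contrast (assumption: means of 150 and 240 weeks).** 1.040/1.025 = 1.015, so the ratio of the two rates shifts by about 1.5%.

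**The 48-week year.** Read per calendar year, the unit alone multiplies the rate by 336/365.25 = 0.920. Combined with the window, the factor at 240 weeks is 1.025 × 0.920 = 0.943. The two effects cancel at 42/(365.25/336 − 1) = 482 days, about 69 weeks.

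**Re-enrolled subject.** A gap of about 2 years is 104 weeks, and 104/(96 × 240) = 0.45% of planned person-time. Read literally, the TEAE window spans this gap although treatment duration leaves it out.

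**The case against.** The strongest reply is that the effect hardly matters. The rate is pooled, so mean exposure sets the excess, and the plan is for 240 weeks. In the parallel US open-label study the protocol reports a median of 227 weeks; as a rough guide (a median, not a mean), 6/227 = 2.6%. This stands: no passage suggests a pooled or subgroup mean near 48 or 24 weeks.

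A reader might infer that the rate is worst wherever boys stop early. The documents do not support that. Boys who move to commercial drug need no 6-week visit. Protocol 6.2.1 also lets boys leave because they are eligible for another ataluren study, and SAP 1 describes Canadian boys waiting to enter Study 016; a transfer without a break leaves little or no off-drug time. The number of early stoppers with a full window is not given, and without one the pooled excess is no larger than for completers.

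A reader might also infer that comparisons by ambulatory status are distorted. No passage says that exposure differs by that factor, and with one arm there is no treatment contrast to bias.

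It can also be said that days on drug is the natural denominator for a rate called exposure-adjusted, that the rule is stated openly, and that the error overstates harm rather than hiding it. All true, but none of this puts the two parts on the same period. Limiting the numerator to on-drug events would do so, but would make this table disagree with every other TEAE table.

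**Conclusion.** The mismatch is plain in the text and nothing else in the documents resolves it. In the SAP's 48-week unit it can only raise the rate. The size is small: about 2.5% at 240 weeks and 4% at a mean of 150 weeks, assuming that every boy is followed for the full 42 days and that event rates are equal on and off drug. With shorter observed follow-up, or fewer events off drug, the excess over the on-drug rate is smaller.

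Two stronger readings should be avoided. The rate is not too high per calendar year at the planned duration: the declared 48-week unit more than offsets the window, for a net 5.7% below a matched calendar-year rate. The unit rescales every rate equally, though, so it does not correct an excess that varies with exposure. Nor is this the study's only summary that allows for unequal follow-up, since SAP 5.2 has a censored Kaplan-Meier analysis of time to discontinuation. Any effect on subgroup or cross-study comparisons is possible but not shown; the documents do not say how other ataluren studies computed their rates.

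**What to change.** Add a sentence to SAP 5.7.1 defining one at-risk period for both parts of the rate. Keep all TEAEs, and add to each boy's days on drug his observed days after the last dose, up to 42, ending at the last study contact or at the start of commercial or other-study ataluren, whichever comes first. For the re-enrolled subject, apply the same period to events and person-time: two treatment periods, each followed by up to 42 observed days, with the rest of the gap in neither. State as well whether days on study drug means the treatment duration in SAP 5.6, and head the column as 48-week patient-years.

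The cost is small. The change needs no protocol amendment and relies mainly on last-dose and visit dates already collected; where the start of other ataluren is not recorded, last study contact serves. There is a minor downside: the denominator becomes time at risk rather than pure drug exposure, so the table should be labelled that way. If other ataluren studies divided by on-drug days, show that version alongside to keep the figures comparable.
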